4.3 Restrictions

The following restrictions apply while the patient is receiving study treatment for the specified time before and after:

- 1. Male patients with female partners of child-bearing potential should be willing to use barrier contraceptives (i.e., by use of condoms), during their participation in this study and for 6 months following the last dose of the study drug. Patients should avoid procreation for 6 months after completion of trial treatment. Male patients must refrain from donating sperm during their participation in the study and at least for 6 months after the last treatment. If male patients wish to father children, they should be advised to arrange for freezing of sperm samples prior to the start of study treatment.
- 2. Females of child-bearing potential should use reliable methods of contraception from the time of screening until 6 weeks after discontinuation. Acceptable methods of contraception include total sexual abstinence, tubal ligation, hormonal contraceptives that are not prone to drug-drug interactions (IUS Levonorgestrel Intra Uterine System (Mirena), Medroxyprogesterone injections (Depo-Provera), copper-banded intrauterine devices and vasectomized partner. All hormonal methods of contraception should be used in combination with the use of a condom by their male sexual partner for intercourse. Female patients should not be breast feeding and must have a negative pregnancy test prior to start dosing if of child-bearing potential or must have evidence of non-child-bearing potential by fulfilling one of the following criteria at screening:
 - Post-menopausal defined as aged more than 50 years and amenorrhea for at least 12 months following cessation of all exogenous hormonal treatment.
 - Documentation of irreversible surgical sterilization by hysterectomy, bilateral oophorectomy or bilateral salpingectomy but not tubal ligation.
- 3. All patients must avoid concomitant use of medications herbal supplements and/or ingestions of foods with known potent inducer/inhibitory effects on CYP3A4 activity whenever feasible. Such drugs must have discontinued for a period of 1 week (CYP3A4 inhibitors) or 2 weeks (CYP3A4 inducers) prior to first administration of DZD9008. Guidance on medications to avoid, medications that require close monitoring and on washout periods is given in Appendix H. Patients may receive any medication that is clinically indicated for treatment of adverse events. All concomitant medications should be captured on the eCRF.
- 4. Patients should abstain from eating large amounts of grapefruit and Seville oranges (and other products containing these fruits, e.g., grapefruit juice or marmalade) during the study, e.g., no more than a small glass of grapefruit juice (120 mL) or half a grapefruit or 1 to 2 teaspoons (15 g) of Seville orange marmalade daily.

Date: July 24,2023

- 5. Patients should avoid donating blood whilst participating in studies of DZD9008 and for at least 12 weeks after receiving the last dose of the study treatment.
- 6. Patients who wear contact lens must discontinue wearing their lenses if they have any mild to moderate eye symptoms (CTCAE grade ≤ 2) while receiving treatment with DZD9008 until at least one week after symptoms have resolved. If a patient has a recurrence of eye symptoms or experiences any severe (CTCAE grade ≥ 3) ocular events, they must discontinue wearing their contact lenses until at least one week after treatment with DZD9008 is permanently discontinued. Patients must not use any eye drops or ointment for treatment of eye symptoms, unless agreed by a study doctor, at any time during the study until 1 week after DZD9008 has been permanently discontinued, Patient should consult the clinic promptly if they have any concerns.
- 7. Patients require anticoagulation and anti-platelet therapy, i.e., with Warfarin, heparin etc. while receiving DZD9008 may be at increased risk of hemorrhage. They should be monitored for any signs of bleeding.

For restrictions relating to concomitant medications, see next Section 4.3.1.

4.3.1 Concomitant treatment

Information about any treatment within 4 weeks prior to starting of DZD9008 and all concomitant treatments given during the study along with reasons for the treatment will be recorded in the Case Report Form (CRF). After permanent discontinuation of DZD9008 and 28 day follow up, only subsequent regimens of anti-cancer therapy will be recorded in CRF. If medically feasible, patients taking regular medication, with the exception of potent inhibitors and inducers of CYP3A4 (see Section 4.2 and Appendix H), should be maintained on it throught the study period.

All patients must avoid concomitant use of medications, herbal supplements and/or ingestions of food with known potent inducer/inhibitory effects on CYP3A activity whenever feasible. Traditional Chinese Medicine should be avoided. Such drugs must have been discontinued for 1 week (CYP3A4 inhibitors) or 2 weeks (CYP3A4 inducers) prior to first administration of DZD9008. Guidance on medications to avoid, medications that require close monitoring and on washout periods is given in Appendix H.

Patients must avoid live vaccines whist receiving study drug and up to 30 days after the last dose of study drug.

Patients may receive any medication that is clinically indicated for treatment of adverse events. All concomitant medications should be captured on the electronic CRF (eCRF).

Other anticancer agents, investigational agents and radiotherapy should not be given while the patient is receiving DZD9008. The patient may be allowed to take localized palliative radiotherapy only if it has been confirmed local lesion is not progressing, and/or after overall response has been evaluated as disease progression. This is to avoid interfering tumor assessment in the event of disease progression. Study drug interruption is not required in the case of local palliative radiotherapy for pain control (excluding chest and brain). For local

Date: July 24,2023

palliative radiotherapy to chest and brain, study drug should be interrupted during and up to 7 days post the palliative radiotherapy. Definitive radiotherapy and other anticancer therapy is not allowed.

Blood transfusions and hematopoietic growth factors are allowed as clinically indicated during the study but not during the screening phase (Part A escalation only) to support blood cell count for eligibility and the DLT assessment period (Cycle 1 in Part A) when transfusions should not be administered unless the patient experiences a hematological DLT or require emergency treatment for any condition.

Patients may receive treatment with corticosteroids and/or bisphosphonates for the treatment of bone metastases. Patients may also receive radiotherapy for painful bony metastases.

Supportive care and other medications that are considered necessary for the patient's well-being, may be given at the discretion of the investigator.

5. STUDY TREATMENT AND CONDUCT

5.1 Treatment

Supply, Packaging and Labeling of DZD9008

DZD9008 drug substance and drug product to be used for this clinical study are manufactured in accordance with Good Manufacturing Practice (GMP).

DZD9008 will be supplied by Dizal as 25 mg, 50 mg, 100 mg, 150 mg and 200 mg tablet by IRT system.

Labels will be prepared in accordance with GMP and local regulatory guidelines. The labels will fulfil GMP requirements for labelling. Label text will be translated into local language.

The label will include the Name of the Sponsor, Study Code, for clinical trial use only and /or any other specific requirements.

DZD9008 tablets of 25 mg, 50 mg, and 100 mg strengths are presented as yellow, round shaped, biconvex, and film-coated tablets. Each HDPE bottle contains 25 units of one strength of the above mentioned 3 different tablets, and with 1 g of pre-packed silica-gel. DZD9008 tablets of 150 mg and 200 mg strengths are presented as yellow, caplet shaped ,biconvex ,and film-coated tablets, with debossing of either the "150 mg" or "200 mg" on one side and the company logo on the other side. The tablet core is off-white to pale yellow after removing the coating film. Each HDPE bottle contains 30 units of one strength of the mentioned 150 mg or 200 mg tablets, and with 1 g of pre-packed silica-gel.

DZD9008 tablet must be stored at storage condition of up to 30 °C in the original container(s). The stability study of DZD9008 clinical batches is on-going and will be continued to at least cover the whole clinical trial. The shelf life will be evaluated when stability data becomes available.

All study drugs should be kept in a secure place under appropriate storage conditions. The investigational product label specifies the appropriate storage condition.

Date: July 24,2023

Drug administration

DZD9008 will be given orally, once daily except for Cycle 0 in Part A dose escalation and food effect cohort.

In Part A dose escalation cohort and dose expansion cohorts 1 and 2, patients are required to keep a fasted condition for \geq 1 hour prior to and \geq 2 hours post dosing. Water is permitted during this fasted period.

In Part A dose expansion cohorts 3 - 6, patients are recommended to take DZD9008 with a low-fat meal. The low-fat meal is defined as approximately 400 to 500 Kcal with about 25% of calories comes from 11 - 14 grams of fat. Meal record will be collected at clinic site on PK sampling days as described in Table 7. Compliance with prandial conditions for non-PK sampling days is to be confirmed by the study personnel during the study visits (e.g., through patient diaries).

In Part B, patients will receive repeat daily dosing of DZD9008 at 200 mg and 300 mg with food to further investigate its anti-tumor efficacy, safety/tolerability and PK.

Following review and approval from IEC/IRB and/or local regulatory authority (as applicable) on the optimal RP2D selection (i.e., dropping the suboptimal dose), patient who is under screening will start treatment at optimal dose level. Patient who has been enrolled in optimal RP2D cohort can stay and maintain the pre-defined treatment course. The ongoing patient who has been randomized to another (suboptimal) Part B dose cohort can maintain the same dose level, or shift to receive the optimal dose if (a) judged by the investigator that it is of the best clinical benefit to patient; (b) patient's re-consent is obtained.

Dose should be taken approximately 24 hours apart at the same time point each day. On PK and plasma ctDNA sampling day, the dose should be instructed to take by site personnel. Doses should not be missed. If a subject misses taking a scheduled dose, within a window of 12 hours, it is acceptable to take the dose. If it is more than 12 hours after the dose time, the missed dose should not be taken and should be recorded, and subjects should be instructed to take the dose at the next scheduled time. If a subject vomits after taking their DZD9008, they should not make up for this dose.

Enrollment of patients into Part A dose expansion cohort 5 will be triggered when emerging data shows DoR reaches 6 months.

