- Higher incidence of dose reduction and interruption occurred at 400 mg cohort was observed as compared to 200 mg and 300 mg cohort, which presumably led to lower clinical efficacy at the 400 mg cohort (ORR 25% at 400 mg). As the doses of 100 mg or above demonstrated clinical activity, and 200 mg or 300 mg is expected to overcome PK variability of DZD9008 to achieve pharmacological relevant exposure required from different subtypes of Exon20ins, thus selecting both 200 mg and 300 mg is appropriate to further evaluate DZD9008 dose optimization for the phase 2 pivotal study.
- DZD9008 elimination half-life is approximately 50 hours following a single dose across the doses investigated, which supports the once daily dosing regimen of DZD9008 in clinical development.

Ethnic sensitivity

 Based on the available data, no obvious difference in safety, PK and anti-tumor efficacy of DZD9008 was observed between Asian and White patients across different regions/countries. Therefore, Dizal believes that the use of same dose and schedule across different regions and countries is appropriate.

Patients enrolled to Part B will receive repeated dosing of DZD9008 at 200 mg or 300 mg once daily. Following review and approval form IEC/IRB and/or local regulatory authority (as applicable) on the optimal RP2D selction, eligible patients can be enrolled into the optimal RP2D cohort. The ongoing patients previously randomized to the suboptimal Part B dose cohort can maintain the same dose level, or shift to receive the optimal RP2D, if judged by the investigator that it is of the best clinical benefit to patients and re-consent is needed (see section 5.1). DZD9008 will be administrated with food as dosing with high fat food in Part A showed limited effect on DZD9008 exposure. Patients with prior therapy may be stratified into subcohorts when data is analyzed.

Patients will receive repeated daily dosing of DZD9008 until disease progression, intolerable AEs, discontinuation criteria have met or withdrawal of consent.

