5.1.5 Toxicity management and dose modifications

If a patient experiences a CTCAE ≥ grade 3 and/or unacceptable toxicity including a DLT not attributable to the disease or disease-related processes under investigation, where the investigator considers the AE of concern to be specifically associated with DZD9008, dosing should be interrupted and supportive therapy will be administered as required in accordance with local practice/guidelines.

If the toxicity does not resolve to \leq CTCAE grade 2 within 21 days, then the patient should be withdrawn from the study and observed until resolution of the toxicity.

If the dose reduction is due to drug related AE, the dose is not allowed to escalate back to the original level after AEs resolve.

On resolution of toxicity within 21 days during treatment, DZD9008 may be restarted at the same dose or a lower dose:

Date: July 24,2023

- If a further episode of the same AE subsequently requires dose interruption, patient should restart at one dose level lower (except cohort 1 dose, restart at cohort 1 dose level). (Refer to Table 3). For cohort 2 of Part B, the dose could be reduced to 200 mg and then 150 mg if needed; for cohort 1 of Part B, dose could be reduced to 150 mg).
- If a different AE subsequently requires dose interruption or no prior AE related dose interruption, DZD9008 may restart at same dose level or one dose level lower (unless in Part A Cohort 1, when restart will be at Cohort 1 dose) on improvement of the AE at the discretion of the Investigator.
- Patients who are at the lowest possible dose, and who have demonstrated clinical benefit and an acceptable recovering of AEs to the dose interruption may be permitted to restart at the lowest dose level at the discretion of the Investigator.
- After a second occurrence of CTCAE grade 4 AE, patient must be permanently withdrawn from study treatment (France and Canada only).

Patients with QTc prolongation fulfilling the following criteria (i.e., confirmed QTc prolongation to > 500 msec absolute or a > 60 msec increase from baseline) should have study treatment interrupted and regular ECGs performed until resolution to baseline. If the toxicity does not resolve to \le grade 1 within 3 weeks, the patient will be permanently withdrawn from study treatment. Patients who develop QTc interval prolongation with signs/symptoms of life-threatening arrhythmia will permanently discontinue DZD9008.

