5.2.2.7 Hematopoietic effects

Patients with inadequate bone marrow reserve as demonstrated by any of the following laboratory values (absolute neutrophil count $< 1.5 \times 10^9/L$; platelet count $< 100 \times 10^9/L$; hemoglobin < 90 g/L)

Date: July 24,2023

will be excluded from the study. Hematological parameters will be monitored prior to administration of the first dose, weekly during the first cycle of multiple dosing, at the start of each subsequent cycle, and at discontinuation.

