6.3.4 Laboratory safety assessment

Blood and urine samples for determination of clinical chemistry, hematology and urinalysis will be taken at the visits as indicated in the Study Plan (see Table 11, Table 12, Table 13, Table 14). Laboratory tests do not need to be repeated at baseline if the baseline visit is within 7 days of the screening sample.

Blood and urine samples for safety assessment will be collected at the following times:

- Screening
- First dosing day (Cycle 0 Day 1) for dose escalation: pre-dose (baseline)
- On day 1 and day 9 of food effect cohort in Part A: pre-dose (treatment time might be updated upon emerging human PK data).
- First day of multiple dosing (Cycle 1 Day 1, both Part A and Part B): pre-dose
- Multiple dosing, day 8 and 15 of Cycle 1 (both Part A and Part B): pre-dose
- On Day 1 of each subsequent cycles: pre-dose
- Discontinuation visit

The date of each collection will be recorded in the appropriate CRF.

Following review of data from a group of patients the timing of blood samples may be adjusted for subsequent groups of patients. Additional sampling times may be added if indicated by the emerging data.

Laboratory values that meet the criteria for CTCAE 5.0 grade 3 or have changed significantly from baseline and are considered to be of clinical concern will be repeated/confirmed within 7 days and followed up as appropriate.

The following laboratory variables (Table 4) will be measured:

Table 4 Laboratory variables to be measured

Clinical chemistry	Hematology
Serum (S)/Plasma (P)- Albumin	Blood (B)-Hemoglobin
S/P-Alkaline phosphatase	B-Hematocrit
S/P-ALT	B-Platelet count
S/P-AST	B-Reticulocyte
S/P-Bicarbonate	B-Red blood cell count
S/P-Urea nitrogen	B-White blood cell count
S/P-Calcium	B-Absolute leukocyte differential cell count:
S/P-Creatinine	 Basophils
S/P-Glucose	 Eosinophils
S/P-Potassium	 Lymphocytes
S/P-Magnesium	 Monocytes
S/P-Sodium	 Neutrophils
S/P-Total bilirubin	
S/P-Total serum protein	Coagulation
S/P-Lipase	APTT
S/P-Amylase	INR
S/P-Creatine phosphokinase	
Urinalysis	
U-Glucose	
U-Protein	
II-Blood	

U-Blood

For Italy only, the female subject should only be included or continue receiving study treatment after a confirmed menstrual period and a negative highly sensitive urine or serum pregnancy test upon local practice.

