6.3.5 Other safety assessments

6.3.5.1 Resting 12-lead ECG

Twelve-lead ECGs will be performed at the visit indicated in the Study Plan (see Table 11, Table 12, Table 13, Table 14).

Twelve-lead ECGs will be recorded at the following times:

Part A

Screening

^{*} Beyond what listed in the table, additional urine/serum samples will be collected from all females of childbearing potential at screening (within 7 days of the first dosing), and at treatment discontinuation for a pregnancy test.

Date: July 24,2023

- First dosing day (Cycle 0 Day 1) for dose escalation: pre-dose, 1, 2, 4, 6, 10 and 24 hours post-dosing
- On day 1 and day 9 of food effect cohort in Part A: pre-dose, 1, 2, 4, 6, 10 and 24 hours post-dosing (treatment time might be updated upon emerging human PK data).
- First day of multiple dosing (Cycle 1 Day 1): pre-dose, 1, 2, 4, 6, 10 and 24 hours post-dosing
- Cycle 1 Day 8 and Day 15: pre-dose, 1, 2, 4, 6, 10 and 24 hours post-dosing
- On Day 1 of each subsequent cycles: one assessment at any time during the day
- On occurrence of any cardiac AE
- Discontinuation visit

Part B

- Screening:
 - For sparse PK group: any time on that day for sparse PK group
 - For intense PK group: pre-dose, 2, 4, 6 and 8 hours post dosing (Since there is no dosing at screening, ECG recording should start at a time that would be consistent with planned dosing times at Cycle 1 Day 1 and Cycle 3 Day1 (for baseline purpose).
- Cycle 1 Day 1 and Cycle 3 Day 1: Pre-dose, 2, 4, 6 and 8 hours post-dosing
- Cycle 1 Day 8 and Cycle 1 Day 15: Pre-dose
- Cycle 2 Day 1: Pre-dose
- On Day 1 of each subsequent cycles after Cycle 3: one assessment at any time during the day
- On occurrence of any cardiac AE
- Discontinuation visit

The timing and number of ECGs may be adjusted depending on the emerging PK and safety data.

A 30 minute window will be allowed for ECGs performed at pre-dose and 15 minute window for 1-10 h, and 1 hour window for ECG performed at 24 hours.

Date: July 24,2023

Twelve-lead ECGs will be obtained after the patient has been resting semi-supine for at least 10 minutes prior to times indicated. All ECGs should be recorded with the patient in the same physical position. For each time point three ECG recordings should be taken at about 5 minute intervals. A standardised ECG machine should be used and the patient should be examined using the same machine throughout the study if possible.

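### The Part B shift from 200 mg to 300 mg has no tolerance condition, and adverse events arising at 300 mg after it are tabulated under 200 mg

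*Protocol*

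**What the plan says.** **The shift.** After approval of the dose selection, protocol section 5.1 lets a patient in the dropped cohort stay on the same dose or "shift to receive the optimal dose if (a) judged by the investigator that it is of the best clinical benefit to patient", provided the patient consents again. Section 5.1.4 repeats the rule: "or shift to receive the optimal RP2D, if judged by the investigator that it is of the best clinical benefit", with re-consent. Neither section mentions tolerance of the current dose. SAP 3.3 cites a shift from 200 mg to 300 mg as an example of a dose modification. SAP 5.6.1 keeps the two-stage test for 300 mg and makes the 200 mg statistics descriptive.

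**Toxicity rules (5.1.5).** The one bar on going up reads: "If the dose reduction is due to drug related AE, the dose is not allowed to escalate back to the original level". Dosing is interrupted for a drug-associated event of grade 3 or higher. If it resolves to grade 2 or lower within 21 days, treatment may resume. For a different event, "or no prior AE related dose interruption, DZD9008 may restart at same dose level or one dose level lower". A patient meeting a QTc criterion "should have study treatment interrupted and regular ECGs performed until resolution to baseline", and no reduction is prescribed.

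**Monitoring.** Safety samples are taken at "Multiple dosing, day 8 and 15 of Cycle 1 (both Part A and Part B): pre-dose", and after that on Day 1 of each 21-day cycle. Section 5.2.2.7 sets the same rhythm for hematology: "weekly during the first cycle of multiple dosing, at the start of each subsequent cycle, and at discontinuation". Day 8 and Day 15 vital signs and ECG also belong to Cycle 1 (6.3.3, 6.3.5.1). Later ECGs follow the rule "On Day 1 of each subsequent cycles after Cycle 3: one assessment at any time during the day".

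**Reporting.** Protocol 7.9.3 and SAP 3.3 assign adverse events after a dose modification to the initial dose.

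**The concern.** A rise from 200 mg to 300 mg within a patient is a dose escalation. The protocol reports that gastrointestinal events become more frequent and more severe as exposure rises (5.1.4), so tolerance of the lower dose is the natural thing to ask about first. As written, one investigator may raise a patient who has had a drug-related grade 3 event at 200 mg, another may decline, and both comply.

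The second issue is what the safety tables will show. If events that arise at 300 mg are counted under 200 mg, the two columns are compared less cleanly than their labels suggest. The protocol also says the Part B results are meant to support a submission for accelerated approval.

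**Working it through.** The plan states no figure on this point, so there is nothing to reproduce. The check sets the rules side by side, with a little arithmetic.

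**1. A patient followed through 5.1.5.** A patient on 200 mg has a first drug-related grade 3 event.
- Dosing is interrupted. The event falls to grade 2 within 21 days, and 200 mg is resumed, which the restart rule allows.
- No reduction has taken place, so the bar on re-escalation is not triggered.
- The stopping rules (interstitial lung disease, corneal ulceration, an event unresolved at 21 days, QTc prolongation with signs of life-threatening arrhythmia, a second grade 4 event in France and Canada) do not apply to one resolved event. The forced reduction needs a further episode of the same event.
- The two conditions in 5.1 can now be met, possibly with grade 2 toxicity still present.

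A patient interrupted for a QTc criterion who recovers reaches the same position.

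**2. Part A compared with Part B.** In section 5.1.1.6 the Safety Review Committee may approve moving ongoing patients to a higher dose level, on condition that it is well tolerated. The Part B shift requires neither committee approval for the individual patient nor tolerability.

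**3. Exposure against the visit schedule.** Inputs: doses of 200 and 300 mg; exposure approximately proportional to dose (2.3.5); half-life about 50 h (6.4.3.1); cycles of 21 days with a window of ±2 days (Table 14).
- Dose ratio: 300/200 = 1.5, so steady-state exposure also rises about 1.5-fold.
- Share of the rise reached after t hours: 1 − 2^(−t/50).
- Day 7 (168 h): 1 − 2^(−3.36) = 0.903.
- Day 14 (336 h): 1 − 2^(−6.72) = 0.991.
- Five half-lives: 5 × 50 h = 250 h = 10.4 days.
- Scheduled laboratory, vital-sign and ECG visits before the next Day 1: two (Days 8 and 15) for a patient who starts treatment at 300 mg; none for one who shifts on Day 1 of Cycle 2 or later, whose next visit falls 21 days on (19 to 23 with the window).

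The new steady state is therefore essentially reached before the next scheduled check. Twenty-one days is the longest nominal gap, because a mid-cycle shift meets the next Day 1 sooner.

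**4. Tabulation.** SAP 5.7.1 summarises treatment-emergent events by treatment group and plans no table by dose at onset. Individual listings of events and of dose modifications (protocol 7.9.2) would allow the events to be separated by hand. SAP 5.5 has a relative dose intensity category above 100%, measured against the dose assigned at the start (SAP 4.1). The exposure tables can therefore reveal the raise, while the adverse event tables cannot.

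**The case against.** Much can be said for leaving the text alone.
- An investigator who knows of a grade 3 event will ordinarily weigh it when judging best clinical benefit. The patient consents again, and ethics or regulatory approval of the dose selection comes first.
- A repeat of the same event that needs interruption forces a step down.
- New patients start directly at 300 mg, and the protocol reports good tolerability up to 400 mg (5.2.3). Day 8 and Day 15 visits serve patients new to the drug, whereas a shifting patient has a known history on it.
- Attribution to the initial dose is pre-specified, and SAP 3.3 names this very shift.

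A reader might infer that shifted patients go unmonitored. The documents do not support that. PRO-CTCAE, with its gastrointestinal items, and FACIT GP5 are collected weekly to the end of Cycle 6. Adverse events are collected throughout. Sections 6.1 and 6.3.3 to 6.3.5 allow schedules to be adjusted or checks added. What stands is narrower: no laboratory tests, vital signs or ECG are newly scheduled, and questionnaires do not replace them.

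A blanket exclusion of anyone ever interrupted would also go too far. It would deny the selected dose after one brief resolved event in patients whom 5.1.5 considers fit to resume.

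None of these arguments supplies a tolerance condition or an adverse event table by dose at onset.

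**Conclusion.** The point holds as a cheap improvement, with medium confidence. In the visible text, a patient interrupted but not reduced at 200 mg may be raised to 300 mg without any tolerance condition, and events that arise at 300 mg will be tabulated under 200 mg.

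**Size.** The dose rises 1.5-fold, with up to about 21 days to the next scheduled laboratory, vital-sign and ECG check. The effect on the 200 mg safety tables cannot be quantified, because the documents do not give the number of patients who shift.

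Three stronger readings are not supported.
- A reader might infer that patients already reduced to 150 mg for toxicity can go to 300 mg. Section 5.1.5 forbids a return even to the original 200 mg, so its evident intent bars 300 mg. This is an inference, since the shift is not named there.
- A reader might infer that patients with a previous grade 3 event at 200 mg inflate that arm's overall rate of grade 3 or higher events after shifting. They are already counted there, because SAP 5.7.1 counts each patient once per category. For them only individual preferred-term or organ-class rows could change. A patient whose first such event arises at 300 mg would add to the 200 mg count.
- A reader might infer that the primary result is compromised. SAP 3.4 analyses patients by initially assigned dose, so shifted patients do not enter the 300 mg ORR test.

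**Limits.** Figure 3 of the protocol and the dose-dropping memo of July 27, 2023, listed in SAP section 1, are not visible and could contain a condition. That 200 mg is the dropped dose is read from SAP 3.3 and 5.6.1.

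**What to change.** 1. **Protocol 5.1 and 5.1.4.** Add a third condition: (c) the patient is currently tolerating 200 mg, with no unresolved drug-related adverse event above grade 1; a patient with a prior drug-related event of grade 3 or higher, or a QTc criterion of section 5.1.5, at 200 mg may shift only after agreement with the Sponsor Study Physician; section 5.1.5 prevails.
2. **SAP 5.7.1.** Add a table of treatment-emergent events in shifted patients by dose at onset, and a 200 mg summary that stops counting events at the shift. The planned tables by initial dose can stay.
3. **Optional, Table 14.** Add a footnote for one check of laboratory tests, vital signs and ECG about 7 to 14 days after the shift, when roughly 90% to 99% of the exposure rise has occurred.

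**Cost.** One clause in two places and one or two extra tables. Slightly fewer patients shift, or some shift later. Those who do not may stay on 200 mg, which 5.1 and 5.1.4 already allow. The optional check adds one short visit per shifted patient.
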